6.2.2.4 Submental Skin Laxity Grade (SMSLG) Score

The change from baseline in ALJDS, CR-SMFRS, PR-SMFRS, and SMSLG will be analyzed using paired t-test (or Wilcoxon signed-rank test if normality assumptions are not met). Descriptive statistics and 95% confidence intervals will be presented. As exploratory endpoints, CR- and PR SMFRS will be summarized at each Belkyra treatment visit beside those mentioned three critical visits’

For FACE-Q™ satisfaction with lower face and jawline score, appraisal of neck, and appraisal of area under chin, descriptive statistics of the Rasch transformed scale score will be provided. The Rasch transformed scale score, ranging from 0 (worst) to 100 (best), is derived for the responses for each of the three FACE-Q™ items. The change from baseline in Rasch transformed scale score will be analyzed using paired t-test and 95% confidence intervals will be presented.

The distribution-free 95% CI for the estimate of median (or median change) will be calculated using SAS® procedure Proc Univariate.

[REDACTED]

[REDACTED]

[REDACTED]

[REDACTED]

[REDACTED]

[REDACTED]

[REDACTED]

[REDACTED]

[REDACTED]

[REDACTED]

[REDACTED]

[REDACTED]

[REDACTED]

6.2.3.2 Biopsy Sub-study

Subjects who consent to participate in the optional Biopsy Sub-study will have a biopsy sample collected at least 4 weeks prior to the first BELKYRA treatment at Visit B1. A second biopsy sample will be collected 8 weeks following the last BELKYRA treatment at Visit B2. Biopsy samples, approximately 2 mm, will be excised from the submental area approximately 1.5 cm from the submental crease and 1.5 cm left and right of midline.

- Objective: Evaluate changes from baseline to last BELKYRA® treatment based on histological evaluation of the submental tissue biopsies.
- Analysis: For each biopsy sample, mean levels of pro-collagen I, collagen I, collagen III, and elastin will be evaluated. For each subject, changes in expression from baseline to after final BELKYRA® treatment will be calculated for each marker. The mean change across all subjects for each marker will be determined. Statistical comparisons from baseline to after final BELKYRA® treatment (based on mean change) may be performed to determine the significance of these observations.

Refer to Appendix I for Analysis Plan of Biopsy Data

6.2.3.3 Image Analysis

Standardized facial photographic images using the VECTRA M3 camera system will be captured at the investigative sites prior to each study treatment (BELKYRA and VOLUMA), within 60 minutes of VOLUMA treatment and at the end of study visit. Once the images are submitted to and received at Canfield Scientific, the images will be staged into its digital monitoring system (DMS) and available for review by the Clinical Services Project Management Team (CSPMT). The CSPMT member assigned to monitor the study will review all the images for photographic quality.

All images selected for analysis will be assigned a random tracking number by the CSPMT which will blind the Image Analysis Technicians (IATs) to information such as Subject Secondary Identifier, Visit Name, Image Date, and/or Treatment Group.

Image Analysis (IA) using Canfield Scientific software or scripts will be performed on two dimensional (2D) and three dimensional (3D) images by the IAT(s) on a rolling basis. to provide left and right jawline and submental volume, submental surface area, submental strain, and submental direction movement as well as facial angle measurements on the frontal view image. The 3D image analysis data will measure major and minor strain, displacement in the x, y, and z-directions, and surface area within the submental area of interests (AOI); while the 2D image analysis data will measure subject's two facial angles and submental angle.

Descriptive statistics will be provided for the 3D and 2D image analysis data.

Refer to Appendix II for Analysis Plan of Imaging Data

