Approximately 50 male and female subjects will be treated in the study, out of which approximately 10 subjects are expected to participate in the Biopsy Sub-study. Data collection on participants may continue from a minimum of 12 weeks and up to approximately 64 weeks, depending on the number of BELKYRA injections needed and participation in the Biopsy Sub-study.

There will be no interim analysis. One final analysis is planned for this study. The final analysis will be performed upon the completion of the study. Database lock will be executed for the final analysis.

2. Primary Study Objectives and Design

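### Rolling measurement of the photographs ties reading time to visit, so drift in technician or software can enter the change from baseline for measures read from a single image

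*SAP*

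**What the plan says.** SAP 6.2.3.3 (Image Analysis) has photographs taken "prior to each study treatment (BELKYRA and VOLUMA), within 60 minutes of VOLUMA treatment and at the end of study visit". The vendor's project management team reviews them for photographic quality. Images chosen for analysis then receive a random tracking number, whose purpose is to "blind the Image Analysis Technicians (IATs) to information such as Subject Secondary Identifier, Visit Name, Image Date, and/or Treatment Group".

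The next paragraph says that the analysis "will be performed on two dimensional (2D) and three dimensional (3D) images by the IAT(s) on a rolling basis". The measures fall into two groups:
- 3D: "The 3D image analysis data will measure major and minor strain, displacement in the x, y, and z-directions, and surface area". Jawline and submental volume are also named as outputs.
- 2D: "the 2D image analysis data will measure subject's two facial angles and submental angle".

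The planned analysis is short: "Descriptive statistics will be provided for the 3D and 2D image analysis data". Detail is referred to Appendix II, whose content is not in the text available for this review. SAP section 1 adds: "There will be no interim analysis. One final analysis is planned for this study".

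**The concern.** Protocol 5.1.3 describes a single-arm, open-label study, and protocol 10.5 compares post-treatment values with the subject's own baseline. In such a design nothing subtracts a change in how the measurement is made. If baseline images are read early and exit images late, a shift in landmark placement, in the outline of the area of interest or in the script version looks the same as a treatment effect.

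The rule also works against the masking in the preceding paragraph. The first images to reach the technicians can only be pre-treatment images, and the last are mostly post-treatment. A technician who knows how far the study has run can often guess the visit without seeing the date.

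At stake is the credibility of the image results. They are masked measurements in a trial whose primary endpoint is the Investigator's own open-label rating, so readers may lean on them even though they are only descriptive.

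**Working it through.** **Plan's own figure.** The documents give no calculation for the image data. The only design calculation is in protocol 10.7: a half-width of 14.0% for a 95% interval with 40 subjects at a rate of 78%. It is reproduced to about 0.2 points (exact interval at 31/40: 13.8%; Wald with continuity correction: 14.1%). The present point does not touch it. It supplies n: 50 enrolled × (1 − 0.20) = 40.

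**1. Gap between the two readings.** Inputs, from protocol 3.1 to 3.3 and 5.1.1:
- k BELKYRA treatments, k = 1 to 6, at least 8 weeks apart
- VOLUMA 8 weeks after the last of them
- an optional touch-up 2 weeks later
- exit 4 weeks after the last VOLUMA treatment
- for biopsy subjects, at least 4 more weeks before VOLUMA

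Weeks from Day 0 to exit = 8k + 4, plus 2 with a touch-up, plus 4 with biopsy.
- k = 1, no touch-up: 8 + 4 = 12
- k = 6, touch-up: 48 + 4 + 2 = 54
- k = 6, touch-up and biopsy: 54 + 4 = 58

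These use the shortest permitted intervals. If images are measured soon after receipt, the two readings are about as far apart as the two images.

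**2. Which measures are exposed.**
- *Read from one image:* the two facial angles, the submental angle and surface area. Here change is a late reading minus an early reading, so drift enters directly.
- *Defined as change against a reference image:* strain and displacement. Both images are presumably processed together, so drift between two separate readings does not enter in this way.
- *Volume:* the derivation is not stated. It is exposed if volume is computed per image.

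**3. What drift would do (illustration).** The documents give no drift rate, so a range is assumed. Let d be the drift in units of the SD of the paired change, the same for every subject, with n = 40.

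SE of the mean change = SD/√40 = 0.158 SD. Shift in standard errors: s = d√40. Coverage of a nominal 95% interval = Φ(1.96 − s) − Φ(−1.96 − s).

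| d | s | Coverage |
|---|---|---|
| 0 | 0 | 0.950 |
| 0.1 | 0.63 | 0.903 |
| 0.2 | 1.26 | 0.756 |
| 0.3 | 1.90 | 0.525 |

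Seen the other way, with no true change the interval would exclude zero with probability about 10% at d = 0.1 and 24% at d = 0.2, against 5% with no drift.

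**4. How much reading order reveals (illustration).** The accrual period is not given. The simulation assumed 50 subjects entering uniformly over the accrual period, 1 to 6 treatments equally likely, a touch-up in half, and images measured on arrival. It gives the chance that a randomly chosen exit image is read after a randomly chosen baseline image; 0.50 would mean that order carries no information.

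| Accrual (weeks) | Chance |
|---|---|
| 13 | 1.00 |
| 26 | 0.98 |
| 52 | 0.90 |
| 78 | 0.82 |

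Images from intermediate visits also pass through the queue and blur this signal.

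**The case against.** The strongest reply is that the SAP never says images are measured as they arrive. It gives no lag from receipt to measurement and no unit for the rolling. Rolling by completed subject would fit the words and would largely meet the concern. Appendix II may fix reading order, software version and repeat readings, and protocol 7.1.6 places instructions for central assessment in a procedure manual. Neither can be checked here, so safeguards cannot be called absent from the plan. This stands, and it makes the point one about what SAP 6.2.3.3 leaves open. It does not remove the point, because the natural reading of the section ties reading time to visit and nothing in its visible text prevents that.

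The image results are also descriptive. SAP 3.3.5 defines descriptive statistics without a confidence interval, and SAP 6.2.3.3 adds none, so the coverage figures concern an interval that the section does not plan. That stands too. A drifted mean change would nevertheless be reported as change after treatment.

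A reader might infer more than the documents support:
- *That every image outcome is contaminated.* Strain and displacement are presumably computed against a reference image.
- *That the masking is broken.* Identifier, visit name and date stay hidden, and staggered entry with 1 to 6 treatments mixes visits in the queue. The masking is weakened.
- *That readings may lie 64 weeks apart.* That figure in the protocol summary is total participation and also depends on the Biopsy Sub-study; the visit rules give 54 weeks, or 58 with the biopsy wait.
- *That the images are the only measurements that are not ratings.* SAP 6.2.3.2 also plans collagen and elastin levels in biopsies.
- *That the Independent Reviewer's ALJDS scores share the problem.* They use photographs (protocol 7.2.1), but the documents do not say that they are read on a rolling basis.

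**Conclusion.** The point holds in a limited form. For the angles, surface area and possibly volume, rolling measurement on its natural reading confounds time of reading with visit, and a single-arm trial cannot separate drift from treatment change. Reading order also erodes the masking that the same section sets up.

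The size of any bias is unknown and may be zero. The figures under the working depend on the assumed drift, on 40 pairs and, for masking, on the assumed accrual. The consequence is confined to the descriptive image results: the primary endpoint (the Investigator's live ALJDS rating), the secondary endpoints and the sample size are unaffected. It is worth correcting mainly because the better method costs almost nothing. No interim analysis needs early readings, and photographic quality is checked in a separate step.

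**What to change.** In SAP 6.2.3.3, replace the rolling-basis wording with:

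> Image analysis of a subject starts once the exit image has been received or the subject has left the study. All available images of that subject are then measured in one session, in random order under the random tracking numbers, by the same technician and with one locked software/script version.

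The clause on subjects who have left is needed. SAP 3.3.4 only invites early leavers to an exit visit, and protocol 10.7 allows for 20% who drop out or do not go on to VOLUMA (50 − 40 = 10 subjects). SAP section 6 evaluates BELKYRA in the full analysis population, so their earlier images should still be measured.

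Keep the photographic quality check running as images come in, and align Appendix II with the new text. If rolling readings have already been made, re-measure the archived baseline images, masked and interleaved with the exit images.

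The cost is SAP and vendor wording, with no new images or visits; re-measurement adds technician time only if rolling readings exist. SAP section 1 allows amendment before database lock. The small downside is that measurement is concentrated later in the study, which delays no planned analysis.

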6.3 SubGroup Analyses

As males and females may have differing expectations and perceptions of aesthetic improvement, assessment outcomes of efficacy data will be analyzed by gender.

7. Safety Analyses

All safety analyses will be based on the safety population. Safety will be assessed primarily in terms of the frequency count and the binominal incidence rate of the AEs of interest. The binomial incidence rate for a given event of interest during a certain period is defined as the number of unique patients who have experienced the event of interest in the period divided by the number of patients in the safety population, then multiplied by 100. Note that, for the calculation of the incidence rate, the numerator will be counted at subject level. Specifically, if a subject has experienced the event(s) of interest (at a given summarization level) more than once during the period, he/she will be counted only once into the numerator. The total number of events will also be presented. The 95% confidence intervals (CIs) for binomial incidence rate per the Clopper and Pearson exact method (via SAS procedure Proc Freq) will also be calculated and presented.

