3.3 VOLUMA™ TREATMENT

The initial VOLUMA™ treatment will occur at Visit 4, either 8 weeks after the final BELKYRA® treatment or, if the subject is participating in the Biopsy Sub-study, after the biopsy site has healed. Fourteen days after initial VOLUMA™ treatment, subjects will return to the clinic and the Investigator and subject will assess whether a VOLUMA™ Touch-up treatment is to be performed (Visit 5). The optional Touch-up treatment will occur at Visit 5. All subjects will attend a final Exit Visit 4 weeks after the last VOLUMA™ treatment (Visit 6).

NOTE: If the Investigator and the subject agree that following BELKYRA® treatment, VOLUMA™ treatment is no longer desired or necessary, the subject may exit the study at this time. The subject will be considered as an early discontinuation, and procedures for Visit 6 (Exit Visit) will be performed instead of Visit 4 procedures.

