7.1.8 Injection Site Reaction (ISR) Diary

The ISR Diary will be completed by the subject beginning on the day of treatment with VOLUMA™ and for daily for 4 weeks.

If Touch-up treatment is received at Visit 5, the initial ISR Diary provided at Visit 4 will be collected. A new ISR Diary will be dispensed and started at touch-up treatment. Four weeks of ISR will be collected after the last VOLUMA™ treatment. An example of the ISR Diary is available in *Appendix 11*.

Clinical Study Protocol: CMO-MA-FAS-0513

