10.5.5 Adverse Events

AEs will be coded using MedDRA version 17.0 or higher, and presented by system organ class and preferred term. Treatment-emergent AEs will also be summarized by SAEs, AE severity, AE leading to treatment or study early termination, and relationship to study drugs/devices. Summary tables will be presented by the study treatment drug.

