10.7 DETERMINATION OF SAMPLE SIZE

In the 2 US pivotal trials for BELKYRA® (ATX-101-11-22 and ATX-101-11-23), 79.1% and 77.9% of subjects, respectively, demonstrated a ≥ 1 grade improvement in the CR-SMFRS 12 weeks following the final treatment. In the VOLUMA-002 study, the responder rate defined as the percentage of subjects whose overall mid-face volume deficit improved (i.e., decreased) by ≥ 1 point from baseline based on the average of the 2 blinded Evaluating Investigators'

Clinical Study Protocol: CMO-MA-FAS-0513

assessments at Month 6 using the 6-point Mid-Face Volume Deficit Scale, was 85.6% at Month 6.

In this study, as BELKYRA® and VOLUMA™ will be administered sequentially, the estimated responder rate for the jawline severity is set lower at 78.0%.

The sample size will provide reasonable precision of the estimations of the parameters of interests. With 40 subjects, the half-width of the 95% confidence interval for the proportion of subjects who show ≥ 1 -point improvement from baseline on the ALJDS compared to baseline assessment at the final study visit (after last VOLUMA™ treatment received) is 14.0% assuming the improvement rate is 78%. To account for 20% study drop-out rate and/or subjects who may not continue for the VOLUMA™ treatment, 50 subjects will be enrolled.

The sample size calculation was performed using the PASS 2008 software for one single proportion.

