3.1 Analysis Populations

To adequately describe the statistical analyses, three analysis populations are defined as follows:

- Full Analysis Set (FAS): Consists of all subjects who received BELKYRA.
- Evaluable Set (ES): Consists of the FAS subjects who received both BELKYRA and VOLUMA and a post-treatment efficacy assessment at Visit 6 (Exit Visit).
- Safety Analysis Set (SAS): Consists of all subjects who consented to participation. Includes subjects who are defined as FAS subjects and those subjects who underwent biopsy procedure but did not receive the BELKYRA treatment. This population will be used for safety analyses.

Unless specified otherwise, the FAS will be used for summary of subject disposition, demographics, baseline characteristics, and for efficacy analyses of endpoints that are

assessed up to the end of BELKYRA treatment; the Evaluable Set will be used for the efficacy analyses of endpoints that are assessed at the final study visit, and the Safety Analysis Set will be used for safety analyses.

Note that in the context of the SAP (including the TFL mockup shells), subjects in the safety analysis set are called safety subjects, and subjects in the evaluable set are called evaluable subjects. Also, the terms of full analysis set, safety analysis set and evaluable set mentioned in the protocol are used interchangeably with full analysis population, safety analysis population and evaluable population respectively.

[REDACTED]

[REDACTED]

[REDACTED]

[REDACTED]

[REDACTED]

[REDACTED]

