3.3.5 Other Conventions

Summary statistics (used interchangeably with the term “descriptive statistics”) for continuous data include sample size (N), mean, standard deviation (SD), median, minimum, and maximum. Categorical variables will be summarized using sample size (N), frequency and percentages of patients. In calculating the percentage, unless specified otherwise, the count of subjects “at risk” will be used as denominator. Ordinal variables will be handled as categorical variables in terms of presenting summary statistics.

Subject’s demographic and baseline characteristics, including height, weight, Fitzpatrick skin type and Allergan Jowl Fat Rating Scale (AJFRS) will be collected at Visit 1 (Screening) and the value at Visit 1 (Screening) will be used as baseline value. For efficacy parameters, such as Allergan Loss of Jawline Definition Scale (ALJDS), CR (Clinician-Reported) and PR (Patient reported) Submental Fat Rating Scale (SMFRS) scores, Submental Skin Laxity Grade (SMSLG) score, FACE-Q™ satisfaction with lower face and jawline score; FACE-Q™ appraisal of neck; and FACE-Q™ appraisal of area under chin, baseline value is defined as the assessment outcome taken at Visit 1 (Screening). [REDACTED]

[REDACTED].

Change from baseline is calculated as ‘visit value minus baseline value’. Percentage change from baseline is calculated as change from baseline divided by baseline value, then multiplied by 100. If baseline value is zero, percentage change from baseline will be undefined or not evaluable (NE). If baseline value is missing, percentage change from baseline will be missing.

Data will be pooled across clinical sites/centers for all analyses.

The International System of Units (Système international d'unités or SI) is the current international standard metric system. The SI units will be used for the reporting in all Tables/Figures/Listings for this study.

All statistical analysis and reporting will be performed using [REDACTED].

4. Subject Disposition and Exit Status

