7.4 Other Safety Analysis

Injection Site Reactions (ISR) following treatment with dermal fillers (VOLUMA) will be analyzed using the AE terms captured in the patient diary (i.e. ISR Diary).

ISR events will be tabulated by PT and sorted by descending frequency. If a subject has multiple occurrences (start and stop) of an event associated with a specific SOC and PT, a patient will only be counted once in the incidence count. The total number of events will also be presented.

An overall summary of frequency count and the binomial incidence rate with its associated 95% CIs will be presented to describe ISRs.

The 95% CIs for the binominal incidence rate will be calculated using the Clopper and Pearson exact method.

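### Injection site reaction rates and VOLUMA-related event rates are divided by all consented subjects, including those who never receive VOLUMA, so they come out too low

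*SAP*

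**What the plan says.** SAP section 7 states that all safety analyses use the safety population. It defines the binomial incidence rate as the number of unique subjects with the event "divided by the number of patients in the safety population, then multiplied by 100", with Clopper-Pearson 95% limits. SAP 3.1 defines that population: "Consists of all subjects who consented to participation". It names biopsied subjects who never received BELKYRA as members.

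Sections 7.2 and 7.3 list treatment-emergent AEs and SAEs related to VOLUMA among the incidence categories. For ISRs, section 7.4 says: "An overall summary of frequency count and the binomial incidence rate with its associated 95% CIs will be presented to describe ISRs". None of these sections gives a denominator of its own.

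Four other places bear on the point:

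- **Protocol 7.1.8**, on where ISR data come from: "The ISR Diary will be completed by the subject beginning on the day of treatment with" VOLUMA.
- **Protocol 3.3**, on subjects for whom, after BELKYRA, VOLUMA "treatment is no longer desired or necessary, the subject may exit the study at this time".
- **Protocol 10.7**: "To account for 20% study drop-out rate and/or subjects who may not continue for the VOLUMA™ treatment, 50 subjects will be enrolled".
- **SAP 3.3.5**, which sets a general default: "In calculating the percentage, unless specified otherwise, the count of subjects" at risk is the denominator.

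**The concern.** A subject who never receives VOLUMA has no ISR diary and cannot have a VOLUMA-related event. Counting that subject in the denominator adds a certain non-event and pulls down both the percentage and its confidence limits. In a safety table this error runs in the reassuring direction.

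Safety of the sequence is part of the rationale in protocol 1.2, and SAP section 7 says safety is assessed primarily through these counts and rates. Diary ISRs are the main VOLUMA tolerability result. They are also the outcome most likely to be common, which is where the distortion is largest in percentage points.

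**Working it through.** **Inputs.** From protocol 10.7: 40 subjects for precision, a 20% allowance, 50 enrolled. From SAP section 7: the safety-population denominator and Clopper-Pearson 95% limits. The documents give no expected event counts, so the counts below are assumptions.

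**The plan's own figures.** 40 / (1 − 0.20) = 50, which matches. The stated half-width of 14.0% at 78% and n = 40 is also reproduced closely: 13.7% by Clopper-Pearson and 14.1% by the normal approximation with continuity correction.

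**How many are exposed to VOLUMA.** The 20% covers drop-out as well as non-continuation, and a subject who drops out after VOLUMA still counts as exposed. With 50 treated, the exposed number therefore lies between 40 and 50.

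**Dilution factor.** Reported rate = exposed-subject rate × (exposed / safety set).

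- 50 treated, no untreated consenters: 40/50 = 0.80; 45/50 = 0.90; 50/50 = 1.00.
- 40 exposed, plus an assumed 1 to 3 biopsied-untreated subjects: 40/51 = 0.78 to 40/53 = 0.75.
- 40 exposed, with an assumed 55 to 65 consenters if screen failures are counted: 40/55 = 0.73 to 40/65 = 0.62.

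**Effect on rates and exact 95% limits, 40 exposed in a safety set of 50.**

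| Events (assumed) | Over 40 exposed | Over 50, as written |
|---|---|---|
| 36 | 90.0% (76.3 to 97.2) | 72.0% (57.5 to 83.8) |
| 20 | 50.0% (33.8 to 66.2) | 40.0% (26.4 to 54.8) |
| 4 | 10.0% (2.8 to 23.7) | 8.0% (2.2 to 19.2) |
| 0 | upper limit 8.8% | upper limit 7.1% |

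If all 40 exposed subjects reported an ISR, the table would show 80.0% (66.3 to 90.0) in place of 100% (91.2 to 100).

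**When the reported interval excludes the exposed-subject rate.**

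- 40 exposed: from 29 events. 29/40 = 72.5%, against an upper limit of 71.8% for 29/50. At 28 events, 28/40 = 70.0% and the upper limit for 28/50 is also 70.0%, so the rate is not excluded.
- 45 exposed: from 42 events. 42/45 = 93.3%, against an upper limit of 92.8% for 42/50.

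**Coverage of the nominal 95% interval for the true exposed-subject rate, denominator 50.**

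| True rate | 40 exposed | 45 exposed |
|---|---|---|
| 50% | 79% | 93% |
| 80% | 29% | 83% |

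With the exposed number as denominator, coverage is 96 to 97% in all four cells.

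**BELKYRA-related and overall treatment-emergent rates.** These are affected only if some consented subjects never receive BELKYRA. Protocol 6.1.4 allows biopsied subjects who withdraw before BELKYRA to be replaced so that 50 are still treated, so any such subjects come on top of the 50. With an assumed 2, 25/50 = 50.0% becomes 25/52 = 48.1%.

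**The case against.** The strongest argument is that the ISR denominator is unclear rather than wrong. Section 7 defines its rate for AEs of interest, and protocol 9.1.1.3 handles diary ISRs separately unless they outlast the diary. Section 7.4 names no denominator, so the at-risk default in SAP 3.3.5 might apply. This does not hold up. Section 7 puts all safety analyses on the safety population, and section 7.4 reuses the defined rate and refers to AE terms from the diary. The default gives way wherever something else is specified.

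A second argument is protocol 10.5.5: "Summary tables will be presented by the study treatment drug". By-drug columns could carry by-drug Ns. But that section names no denominator, while SAP section 7 does, and the SAP takes precedence where the two differ.

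Several points do stand:

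- The size is uncertain, and 40 exposed is the extreme of the stated allowance.
- The larger factors need untreated consenters. The second sentence of the safety-set definition mentions only treated and biopsied-untreated subjects, so screen failures may not be counted. BELKYRA-only subjects stay in the denominator on either reading.
- Sections 7.2 and 7.3 promise confidence intervals for the overall summaries. Whether the VOLUMA-related rows also get them is not clear, so the point about limits is firmest for ISRs.
- A rate over everyone who starts the sequence is a legitimate quantity, but it does not describe tolerability of VOLUMA in those who received it.
- Readers could rebuild the exposed-subject rates from the counts and treatment listings. The printed percentages would still be the diluted ones.

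**Conclusion.** The concern holds, and the denominator rule is wrong as written for VOLUMA-specific outcomes. Under the protocol's own 20% allowance, with 50 treated and no untreated consenters, ISR and VOLUMA-related rates are understated by between nothing and one fifth. Anything beyond a fifth depends on assumed numbers of untreated consenters.

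The distortion matters for common ISRs, where the reported interval can exclude the rate actually seen in exposed subjects. For rare related AEs and SAEs the absolute shift is small: 1/40 = 2.5% against 1/50 = 2.0%. The effect on BELKYRA-related and overall treatment-emergent rates is conditional and minor. The primary endpoint, analysed in the Evaluable Set, is not affected. The point should be fixed before the tables are produced, but it does not threaten the study's main result.

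**What to change.** In SAP sections 7, 7.2, 7.3 and 7.4, replace the single denominator with:

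- subjects who received VOLUMA, for diary ISRs and for VOLUMA-related treatment-emergent AEs and SAEs;
- subjects who received BELKYRA (the FAS), for all other treatment-emergent AEs and SAEs, including BELKYRA-, anesthesia- and procedure-related categories;
- all consented subjects, for listings and for pre-treatment or biopsy AEs only.

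Show the exposed N in every table header. In the ISR tables also state how many VOLUMA-treated subjects returned a diary, since a missing diary would otherwise count as no reaction.

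The cost is SAP wording and table-shell denominators, with no new data collection. The only consequence is that some reported rates may be higher.
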